## Amendment History

Protocol Version 2.3 Summary of Changes 01Aug/2017	
Section 1.0 Background and Rationale	No differentiation between patients receiving biopsies vs. those with benign lesions because we will not always be able to determine this prior to the liver intervention procedure. Patients are rather categorized based on recruitment procedure i.e. those that are scheduled for an intervention vs. those undergoing MRI. Indication that the research DCE liver MRI will take less than 10 minutes.
Section 3.0 Patient Sample/Selection	No differentiation between patients receiving biopsies vs. those with benign lesions because we will not always be able to determine this prior to the liver intervention procedure. Patients are rather categorized based on recruitment procedure i.e. those that are scheduled for an intervention vs. those undergoing MRI.
Section 5.0 Research Plan	During personnel training, certain sections of the protocol were found to be repetitive or confusing. These edits are administrative and do not change the study. The language has been streamlined to remove repetition and for better readability. Inclusion criteria and recruitment procedures were updated to remove differentiation between biopsy patients and benign patients.
Section 9.0 Data Safety Monitoring Plan	Addition of the following statement: Very small amounts of MRI contrast agents deposit in certain tissues of the body including regions of the brain, in patients who have received multiple doses of these agents. No known harm has been associated with the deposition, before or since the description of this deposition in 2014. More than 300 million doses of gadolinium contrast have been given in humans since their first use.
Section 10.0 References	References updated to include publication in support of the gadolinium deposition statement (section 9.0)

## **1.0 BACKGROUND AND RATIONALE**

**SUMMARY:** *The primary objective of this study is to develop and validate simultaneous free-breathing 4D fat and water quantification and quantitative dynamic contrast enhanced perfusion in the liver. Secondary aims include developing and validating free breathing quantification of relaxation parameters T1 and T2, and developing and validating a minimal breath-hold (< 8 s) high quality diffusion exam using highly accelerated steady state diffusion imaging sequences. Investigators aim to scan 170 subjects who are scheduled for liver intervention or MRI exam of the liver. The study is greater than minimal risk.*

MR abdominal imaging made up 7% of the 30.2 million MRI examinations performed in the US in 2010, and liver MR is the most common abdominal exam [1]. MRI is extremely important in liver evaluation, where the capabilities to produce multiple and exquisite soft-tissue contrast and readily available multiphasic imaging without radiation risks have been leveraged to make it the technique of choice for lesion characterization. However, liver MR exams are complex, riddled with failures due to motion artifacts, and poor or variable lesion characterization due to small size, motion, and radiologist uncertainty in interpretation.

Almost every acquisition during an MR liver exam requires a breath-hold to limit motion artifacts. However, it is known that sicker patients provide shorter breath-holds [8]. Thus even with current fast imaging sequences, long breath-holds are difficult for patients, and result in non-diagnostic examinations. The direct cost of these exams, the missed diagnoses, the lost patient and physician time, the delays in treatment and inability to treat diseases properly means that the real dollar cost of motion in body MRI is immeasurable.

The second major set of problems with liver MRI is that of obtaining uniformly high quality exams and lesion characterization. Abdominal MRI is notoriously dependent on the quality of technologists because when motion or image quality issues arise, there are a myriad of adjustable parameters that require years of experience to master. The resulting images can be complicated by technical factors such as motion during the exam or simply small lesion size, differences in acquisition parameters and timings between exams, and difficulties in aligning the lesions on different kinds of contrast mechanisms. In the hands of experts, MRI liver characterization is often exquisite and definite, but in the hands of a majority of practicing radiologists, it is far from ideal.

These problems lead to frustration for both referring and interpreting physicians, and more importantly to biopsy of lesions for definitive diagnosis. If liver imaging could be converted to an ultra-fast examination performed at high spatial and temporal resolution, and at the same time provide quantitative information so that image characterization could be objective, the effect on clinical care could be significant. This would eliminate technically compromised exams, improve certainty in diagnosis, diminish the need for repeat or follow-up imaging, and most tantalizingly, potentially decrease the need for invasive tissue diagnosis.

We have developed techniques that we hope can turn the present standard liver examination into a high resolution exam that requires almost no breath-holds, and yet provides quantitative measures of all contrast mechanisms presently employed in the clinical standard examination. The research DCE liver MRI scan time will be less than 10 minutes, completely removing the

technologist competence and patient cooperativeness pieces from the factors that affect exam quality. **Preliminary data:** The novel free-breathing high spatiotemporal resolution DCE liver MRI using non-Cartesian parallel imaging technique for quantitative perfusion mapping was performed on a Siemens 3T Skyra scanner with six subjects, including four healthy volunteers and two patients. A stack-of-spirals trajectory was under sampled in plane with a reduction factor of 6, and reconstructed using through-time non-Cartesian GRAPPA. High-resolution 3D images were acquired with a true temporal resolution of 1.6~1.9 seconds, while the subjects were breathing freely. A dual-input single-compartment model was established to retrieve liver

[figure not shown]

Figure 1

perfusion parameters from DCE-MRI data, which were co-registered using an algorithm designed to reduce the effects of dynamic contrast changes on registration performance. **Results:** Figure 1 shows representative under sampled and reconstructed images acquired from a normal subject at the arterial phase (~20 sec after contrast injection), portal phase (~70 sec) and equilibrium phase (~180 sec). With the automatic edge detection method, about 20-25% of the volumes from each subject were automatically detected by the algorithm to originate from the same position in the respiratory cycle, and thus pre-registered. After registering the remaining frames to the nearest “pre-registered” neighbor, almost no detectable solid organ motion

[figure not shown]
[figure not shown]

Figure 2 a

remained. Figure 2 shows representative time courses of contrast concentration from the aorta, portal vein, and hepatic parenchyma (single

voxel), and the model fit to the parenchymal time-course from a healthy subject. The time course from the liver voxel, same as before registration is also plotted as a comparison. The model fit after registration yielded an arterial fraction (AF), distribution volume (DV) and mean transit time (MTT) of 18.8%, 24.2%, and 4.6 s, respectively, while the same quantities prior to registration were 13.5%, 35.2%, and 10.6 s, respectively. The perfusion parameters after registration are all in good agreement with published literature for CT and MR (3,4,14).

## **2.0 OBJECTIVES**

We hypothesize that a quantitative and near free-breathing MRI approach will lead to improved tissue characterization, resulting in fewer ambiguous readings and thus fewer biopsies. As each component of the proposed methodology has been experimentally validated in our preliminary work, the next appropriate step would be to evaluate the clinical feasibility of the exam. **Our goal is to test the ability of our developed quantitative MRI techniques to provide high quality images of the liver and to differentiate liver lesions from one another in a timeframe shorter than a current clinical exam.**

## **3.0 PATIENT/SAMPLE SELECTION**

We aim to scan at least 170 patients who are scheduled for liver intervention or MRI exam of the liver using the new quantitative protocol, assess the discrimination accuracy of binary classifiers in predicting lesion type, and compare the diagnostic accuracy of the new protocol to the clinical standard.

## **4.0 REGISTRATION PROCEDURES**

If applicable, all patients enrolled on study will be entered into the Oncore database. If samples are being collected, a sample count will be entered into the database.

## **5.0 RESEARCH PLAN**

Our abdominal imaging group performs at least 150-200 MRIs for liver lesions every year. A vast majority of these lesions are HCC or metastatic disease (approximately 40% each), a small number are cholangiocarcinoma (at most 10%) and an additional 10% are benign lesions such as adenomas, hemangiomas, or focal nodular hyperplasia (FNH). Most patients also undergo biopsies to establish diagnosis. For our analysis we will obtain a quantitative dataset of 170 focal liver lesions in which the biopsy or clinical "truth" is known.

### **Inclusion Criteria:**

All patients scheduled for a MRI exam of the liver will be eligible to participate in this study.

1. Patients with known liver lesion
2. Male or female patients, age 18 to 100 years.
3. No contraindications to getting contrast enhanced MRI examinations.
4.  $GFR \geq 40$ .

The study population may include illiterate persons and UH/Case employees if they meet other inclusion criteria. The consent process for these potential participants will be conducted according to IRB guidelines.

### **Exclusion Criteria:**

1. Patients with ferromagnetic or otherwise non-MRI compatible aneurysm clips.
2. The presence of an implanted pacemaker or implanted defibrillator device

3. Patients with contraindications for MRI due to embedded foreign metallic objects. Bullets, shrapnel, metalwork fragments, or other metallic material adds unnecessary risk to the patient.
4. Pregnancy. Regular clinical practice already excludes pregnant patients from gadolinium contrast due to unknown effects on the fetus. The current clinical practice will be applied - patients will be verbally screened and asked if they think they could be pregnant. If the answer is yes, then the patient will be excluded from the study. If the patient is uncertain about the pregnancy status, she will be given an option to undergo a pregnancy test or not participate in the study altogether. Patients who self-report that they are not pregnant will be allowed to participate in the study. This procedure is based on current department policy guidelines.
5. Implanted medical device not described above that is not MRI-compatible;
6. Known history of claustrophobia;
7. Known history of allergic reaction to MR contrast material;
8. Late stage renal failure with estimated glomerular filtration rate (eGFR) of less than 30 mL/min/1.73 m^2 based on patient's serum creatinine due to the significantly increased risk of nephrogenic systemic fibrosis (NSF). ('Past' 3 months timeframe will be used to calculate the eGRF).
9. Minors will be excluded.
10. Prisoners and members of other vulnerable populations will be excluded from this study. The subject selection population will not regularly include prisoners and other vulnerable population members as these populations will not provide any additional unique information to or uniquely benefit from the study. Non-english speaking population will be excluded from the study due to lack of sufficient resources to pay for translator and interpreter services.

### **Recruitment procedures:**

There will be two methods of recruitment. The first method is via referral of patients from the intervention radiology clinic. Secondly, we have a waiver of HIPAA authorization and waiver of consent to identify and contact patients from the out-patient schedule.

The abdominal imaging section runs an intervention radiology clinic where patients with liver lesions are evaluated in order to plan and conduct the liver intervention procedure. All of the physicians at this intervention radiology clinic are co-investigators on the current IRB protocol and have physician-patient relationship with these clinic patients. Upon referral, a member of the research team will approach these patients in person during their pre-procedure evaluation visit and give them an option to participate in the research study. During this visit, the patients will be given information about the research study procedure. The patient will be conveyed the information regarding potential direct and indirect benefits, and risks and discomforts associated with the study. The patients will also be informed that there are no financial charges to them or their insurance for this research scan and that they will receive an amount of \$100 as compensation for participation in the study. All communication with the patient will be conducted in a private area. All of the patient questions regarding the research study will be answered satisfactorily. If the patients wish to participate in the study, they will be consented on the same day (pre-procedure evaluation visit to the clinic) and will be scheduled for research MRI scan before the day of their intervention procedure. The patients will be offered a copy of the signed consent form to take home with them to discuss with their friends and family if they wish to. Only if the patient consents to participate in the research study during the first meeting

and agrees to come in for research MRI in the future, then the study personnel will communicate with the patients by phone to confirm the appointment for research MRI and answer any questions the patient may have at this point. The referring physician/ primary care team will provide the diagnosis to the patients. The research team personnel will not provide any diagnosis to the patient.

We have a waiver of HIPAA authorization and waiver of consent to identify and contact patients from the outpatient MRI schedule.

***Request for waiver of HIPAA authorization and waiver of consent:*** *The investigator will take precautions to protect the subject's privacy and the confidentiality of the data pertaining to his/her participation in this research study. We are requesting a waiver of HIPAA authorization and waiver of consent for contacting the patients in person and not the waiver of the consent for the research study as such. We intend to identify patients on outpatient MRI schedule for a clinically indicated liver MRI and contact them in person. There will be no improper use of or disclosure of PHI under this waiver. Only the research staff will access the PHI for above described purpose. The patient identifiers accessed under this waiver of HIPAA authorization will not be retained. The identifiers will be destroyed on the same day once the purpose of contacting the patients in person is complete. We assure that the PHI will not be reused or disclosed to (shared with) any other person or entity, except as required by law, for authorized oversight of the research study, or for other research for which the use or disclosure of the PHI would be permitted under the Privacy Rule. We are requesting a waiver of HIPAA authorization for contacting the patients in person and not a waiver of informed consent process for the study itself. The patients with benign lesions are typically not biopsied. It is imperative to include a cohort of such patients in the study to increase the diversity of study population and demonstrate the robustness of the new imaging technique. We will use the MRI schedule to identify potentially eligible subjects who are undergoing liver scans. For this purpose, the waiver of HIPAA authorization and waiver of consent is necessary for recruitment. We will not be able to meet our recruitment goals without this waiver, because there is no other way we can contact the patients with benign lesions scheduled for clinical MRI.*

With the waiver of HIPAA authorization and waiver of consent, we will be able to use the MRI schedule to identify subjects who are undergoing liver scans on a given day. On the day of the scheduled clinical MRI exam we will approach the patient in person and give them brief information regarding the research study. The patient will be given information regarding potential direct and indirect benefits, and risks and discomforts associated with the study. The patients will be informed that there are no financial charges to them or their insurance for this research scan and that they will receive an amount of \$100 as compensation for participation in the study. We will ask the patient if he/she is interested in participating in the research MRI. We will request permission from the patient if he/she is willing to be contacted by phone for scheduling a research MRI scan in the future. We will explain it clearly to the patient that he/she will be contacted for participation only if he/she is deemed eligible to participate in the study after discussion with his/her referring physician/primary care team. Thus, the consent for contacting the patients for future participation in research MRI study will be obtained from the patients on the day of their scheduled clinical MRI when the research team member can meet the patient in person. The subjects will not be approached at their doctor's visit. The patients will be

offered a copy of the informed consent form for the actual research MRI to take home with them to study and discuss with family/friends, if desired. All the communication and conversation with the patient will be conducted in a private area. For the research personnel to contact the patient in a manner that is suitable for them, we will ask the patient to provide their contact information (including phone number and/or email address). We will also ask the patients to specify which mode of communication is suitable for them and what time slot of the day is most acceptable if they choose to be contacted by phone. Only if the patient consents to be contacted for research MRI in the future, then the study personnel will communicate with the eligible patients by phone to schedule the study and answer any questions the patient may have at this point

In total, 170 subjects who meet inclusion criteria and who are willing to consent to participation in the study will be recruited.

## **6.0 STUDY PARAMETERS**

MRI of liver using the proposed research technique will be performed on all study subjects. The imaging data will be utilized as a study parameter. This imaging data will be compared with clinical standard imaging and biopsy results of the patient.

## **7.0 CORRELATIVE STUDIES (if applicable)**

N/A

## **8.0 STATISTICAL CONSIDERATIONS**

Ten-fold cross-validation will be used to assess the discrimination accuracy of binary classifiers predicting HCC vs. benign lesions, metastases vs. benign lesions, or metastases vs. HCC [69]. We hypothesize that each classifier will predict non-benign lesions with accuracy (ROC curve area) of at least 80%. With 40 abnormal and 80 benign cases, a one-sided test at a significance level 0.05 testing the null hypothesis that the area under the ROC curve is an uninteresting level of 0.65 vs. the alternative that it is greater than 0.65 will achieve 91% power when the ROC curve area is 0.80 for the new classifier. For a binary classifier discriminating metastases vs. HCC, with 40 cases per group, the power is 84% to test that the area greater than 0.65, when the true ROC area is 0.80 (SAS macro ROCPOWER, [http://www.bio.ri.ccf.org/doc/rocpower\\_help.txt](http://www.bio.ri.ccf.org/doc/rocpower_help.txt)).

In a second step, the diagnostic accuracy of the quantitative protocol will be compared to the standard clinical exam. In each of the cases described above, the three radiologists will be asked to arrive at the most likely diagnosis, by consensus. The quantitative techniques will be similarly used to predict the most likely diagnosis for each lesion. Agreement between the quantitatively predicted “most likely diagnosis” and the actual diagnosis (categorized as HCC, other metastases, cholangiocarcinoma or benign/other) will be estimated and compared to the agreement between the clinical MRI-based diagnosis and true diagnosis using a McNemar test for correlated proportions. With the a sample size of 170, a difference in agreement proportions of 0.75 vs. 0.87 can be detected with 80% power with a two-sided 0.05 significance level test. Funding for Statistical Analysis: [name] will perform the statistical analysis and the grant funding listed for this project covers his time.

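### Section 8.0's 91% power for both benign contrasts assumes 80 benign lesions, but no written target secures them; at the Section 5.0 case mix, power would be about 75%

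*Combined protocol and SAP*

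**What the plan says.** **Power statement (Section 8.0).** Three binary classifiers are planned: HCC vs benign, metastases vs benign, and metastases vs HCC. Each is tested against a null ROC area of 0.65, assuming a true area of 0.80. For the two benign contrasts the basis is "With 40 abnormal and 80 benign cases, a one-sided test at a significance level 0.05", with a stated power of 91%. For the third: "For a binary classifier discriminating metastases vs. HCC, with 40 cases per group, the power is 84" per cent.

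**Case mix (Section 5.0).** HCC and metastases are put at about 40% each and cholangiocarcinoma at no more than 10%; "an additional 10% are benign lesions such as adenomas, hemangiomas, or focal nodular hyperplasia (FNH"). The volume is given as "Our abdominal imaging group performs at least 150-200 MRIs for liver lesions every year".

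**Enrolment (Sections 3.0 and 5.0).** Section 3.0 says "We aim to scan at least 170 patients who are scheduled for liver intervention or MRI exam of the liver". The inclusion criteria open with "All patients scheduled for a MRI exam of the liver will be eligible to participate in this study", followed by a known lesion, age and safety conditions. The recruitment text closes with "In total, 170 subjects who meet inclusion criteria". None of these gives a split by lesion type.

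**Benign patients.** The waiver request in Section 5.0 says of patients with benign lesions: "It is imperative to include a cohort of such patients in the study to increase the diversity of study population". It adds that recruitment goals cannot be met without the waiver. It gives no number.

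**The concern.** The power basis needs benign lesions to be 80/170 = 47% of the sample. The only case mix in the document puts them at 10%. No target, ratio or cap on malignant cases connects the two, so the 91% does not follow from the enrolment as written.

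Two of the three classifier tests depend on the benign group, and telling lesion types apart is part of the goal stated in Section 2.0. If the sample drifts towards the practice mix, the chance of missing a true area of 0.80 rises from about 9% (as stated) to about 25%. Ten-fold cross-validation would have 17/10 = 1.7 benign lesions per fold. A negative benign-vs-malignant result could then reflect too few benign lesions rather than a poor technique.

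**Working it through.** **Inputs.** From Section 8.0: one-sided 0.05 (z = 1.645), null area 0.65, alternative 0.80, group sizes 40/80 and 40/40. From Section 5.0: 170 lesions, with 40% HCC, 40% metastases, up to 10% cholangiocarcinoma and 10% benign. One lesion per patient is assumed.

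**Counts.** The groups implied by Section 8.0 are 40 + 40 + 80 = 160, which leaves 10 of 170 for other lesions. At the Section 5.0 mix, 0.40 × 170 = 68 HCC, 68 metastases, and 0.10 × 170 = 17 each of cholangiocarcinoma and benign.

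**Formula (Hanley-McNeil).** With m abnormal and n comparison lesions, Q₁ = A/(2−A) and Q₂ = 2A²/(1+A):

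SE² = [A(1−A) + (m−1)(Q₁−A²) + (n−1)(Q₂−A²)]/(mn)

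Power = Φ[(0.15 − 1.645·SE₀)/SE₁], with SE₀ taken at 0.65 and SE₁ at 0.80.

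**The plan's own figures.**
- 40/80: SE₀ = 0.0548, SE₁ = 0.0462; (0.15 − 0.0901)/0.0462 = 1.297; power 90.3% (stated 91%).
- 40/40: SE₀ = 0.0614, SE₁ = 0.0498; z = 0.985; power 83.8% (stated 84%).

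Both are within 1 point.

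**At the Section 5.0 mix.**
- 68/17: SE₀² = (0.2275 + 67 × 0.0590 + 16 × 0.0896)/1156, so SE₀ = 0.0697. SE₁² = (0.16 + 67 × 0.0267 + 16 × 0.0711)/1156, so SE₁ = 0.0517. The critical area is 0.65 + 1.645 × 0.0697 = 0.7646, against 0.7401 at 40/80. z = 0.685; power 75.3%.
- 68/68 (metastases vs HCC): SE₀ = 0.0469, SE₁ = 0.0381; z = 1.911; power 97.2%.

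**A smaller benign target.** 55 HCC + 55 metastases + 43 benign + 17 other = 170. For 55/43, SE₀ = 0.0551 and SE₁ = 0.0440; z = 1.348; power 91.1%. For 55/55, power is 93.5%.

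**Sensitivity to the variance form** (null SE for the critical value, alternative SE for power; power in %):

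| Groups | Hanley-McNeil | Same, logit scale | Exact binormal | Closed-form binormal |
|---|---|---|---|---|
| 40/80 (stated 91) | 90.3 | 90.1 | 93.2 | 89.4 |
| 40/40 (stated 84) | 83.8 | 85.1 | 84.3 | 81.4 |
| 68/17 | 75.3 | 79.3 | 68.1 | 68.5 |
| 40/17 | 66.2 | 72.2 | 61.9 | 62.0 |
| 68/68 | 97.2 | 96.4 | 97.4 | 95.8 |
| 55/43 | 91.1 | 91.0 | 90.5 | 88.2 |

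The first two forms fit the stated figures best and give 75-79% at 68/17. The two binormal forms each miss a stated figure by about 2 points or more, and they supply the 68% floor. Hanley-McNeil with the alternative SE throughout gives 94.6% and 91.4% for the two stated cases. It does not match the plan and is left out of the range. The 40/17 row shows the result if only Section 8.0's 40 malignant lesions were used. ROCPOWER, the macro that the plan cites, was not available.

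**The case against.** The best reply is that enrichment was intended. The 10% describes the imaging group's caseload and is not a planned sample. Section 8.0 is conditional on its group sizes. The implied 160 fits within 170 with 10 to spare. The waiver request treats a benign cohort as essential and sets up a route to reach it, and the Data Safety Monitoring Plan still refers to a separate benign-lesion set. Patients on the schedule route are contacted only after discussion with their care team and once a diagnosis has been given.

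Much of this stands. It makes 17 the result of unselected sampling rather than a count that the plan predicts. It does not supply the missing number: none of these texts states how many benign lesions are wanted. The Amendment History explains that patients are now grouped by recruitment route because lesion type cannot always be determined before the intervention procedure.

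A reader might also infer three stronger points that the documents do not support:
- *That 91% is miscalculated.* It is not; 40/80 gives about 90%.
- *That 80 benign lesions cannot be reached.* At 10% of 150-200 MRIs a year there are 15-20 benign cases, so 80 would take 4.0-5.3 years with every case enrolled. But the volume is a stated minimum, and the text reviewed gives no enrolment period for this to contradict.
- *That the whole analysis is underpowered.* Metastases vs HCC gains power at the practice mix, and the McNemar sample-size statement uses the total of 170, not the 40/80 split.

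**Conclusion.** The concern holds as a gap between the power basis and the enrolment text. The 91% is sound for 40 abnormal and 80 benign lesions, but no written step delivers 80. If enrolment followed the Section 5.0 mix, each benign contrast would have about 75% power (75-79% for the two best-fitting forms, 68-79% across the four), and metastases vs HCC about 97%.

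This rests on one lesion per patient, the Section 5.0 shares taken at face value, all 68 malignant lesions being used in each contrast, and Section 8.0's own areas of 0.65 and 0.80. The documents do not show that the investigators expect only 17 benign lesions, and the sample size of 170 need not change. The point should be fixed, but it is a clarification rather than a fatal flaw.

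**What to change.** Reconcile Sections 5.0 and 8.0 in one of two ways.

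**(a) If the practice mix is expected**, add to Section 8.0: *Under the case mix in Section 5.0 we expect about 68 HCC, 68 metastases, 17 cholangiocarcinoma and 17 benign lesions; power for each benign contrast at these counts is [ROCPOWER result].* Expect about 75%. The cost is wording only, with a less favourable stated power.

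**(b) If enrichment is intended**, write the benign target within the 170 into Sections 3.0 and 5.0. It could be the implied 40 HCC, 40 metastases, 80 benign and 10 other. A smaller target such as 55/55/43/17 also gives about 91% for each benign contrast by Hanley-McNeil (88-91% across the four forms), and about 93% for metastases vs HCC. The cost is slower enrolment: at 15-20 benign cases a year with every case enrolled, 43 would take 43/20 = 2.2 to 43/15 = 2.9 years, against 4.0-5.3 years for 80. Because lesion type may be unknown in advance on the intervention route, the target will depend mainly on the schedule route.

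Neither option needs patients beyond 170.
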